Bupropion is an anti-depressant that increases striatal dopamine transmission,¹⁰ improves reward processing¹⁰ and is widely available at a modest cost.¹¹ The standard 300 mg/day dose of bupropion has demonstrated clear efficacy for smoking cessation in various populations.^{12,13} Outside of the smoking literature, high dose bupropion (400-450 mg/day) exhibits superior efficacy relative to the 300 mg/day dose for treating psychiatric disorders,^{14,15} reducing weight and body fat,¹⁶ and alleviating anhedonia,¹⁴ without meaningfully increasing side effects.¹⁷ Thus, high dose bupropion may be particularly effective at promoting smoking cessation in anhedonic smokers, improving anhedonia-related mental health, and preventing post-quit weight gain. To the best of our knowledge, 300 mg/day is the highest bupropion dose tested for smoking cessation in any population to date.

In this continuation proposal, we translate work in the prior period on mechanisms underlying relapse in anhedonic smokers to the development of a novel, disseminable, and putatively effective treatment for this high risk population. We propose a clinical trial in which anhedonic smokers are provided standard cessation counseling and randomized to either: the standard 300 mg/day dose of bupropion (BUP-300; N=150) or a high 450 mg/day dose (BUP-450; N=150). In addition to treatment effects on 7-day point prevalence smoking abstinence (PPA) outcomes, we will: i) examine if improvement in reward processing is a mechanism of action for BUP-450's efficacy with innovative laboratory-based computer task and subjective indices of reward processing, ii) assess moderators of treatment efficacy, iii) investigate treatment effects on secondary mental health and body weight and adiposity outcomes; and iv) utilize the extended release (XL) formulation that requires dosing only once per day, which has yet to be tested for cessation and may increase adherence.

Primary Aims

- 1. To test the efficacy of high dose bupropion for smoking cessation in anhedonic smokers.** Hyp 1. PPA rates across the 6-month post-quit follow-up period will be higher in BUP-450 vs. BUP-300.

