- 2. To test whether treatment-related enhancement of reward processing is a mechanism of action of high dose bupropion.** Hyp 2. The effects of BUP-450 vs. BUP-300 cessation outcomes will be mediated by reward processing, such that dose will predict greater improvements in reward processing, which will in turn be associated with greater odds of abstinence.

Secondary Aims

- 3. To test the effects of high dose bupropion on secondary outcomes of:** (a) anhedonia and related psychopathology (i.e., depressive, social anxiety, ADHD, PTSD symptoms), and (b) change in body weight and percent body fat composition.
- 4. To examine if baseline anhedonia level and related psychopathology (depressive, social anxiety, ADHD, PTSD symptoms) moderate the efficacy of high dose bupropion on cessation outcome.**

If successful, this research may identify a novel, highly-disseminable, cost-effective, and efficacious cessation treatment for an at-risk population, with wide-spanning implications toward offsetting three of the nation's top causes of morbidity and mortality—smoking, mental illness, and health problems due to excessive weight.

A. SIGNIFICANCE

A.1 Importance of Increasing Cessation Treatment Outcomes for Smokers Psychiatric Symptoms

While the overall population-level rate of smoking has significantly declined in recent years, smoking among those with psychiatric symptoms and conditions has remained stable,¹⁸ with SWPS accounting for a mounting proportion of the U.S. tobacco-related disease burden each year.¹ A key source of the tobacco-related health disparities facing SWPS is their disproportionately low quit rates.¹ Hence, improving smoking cessation among SPWS is vital for reducing tobacco-related disparities and counteracting the public health burden of smoking.

A.2 Current Status of Cessation Treatment Development Research for SWPS

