Primary Aim 2: Mediation. Aim 2 will examine slopes from individual piece-wise LGCMs (or raw difference scores when only 2 timepoints available) to model changes in reward processing (see C.6) prior to quit day, the jump from pre to 1-week post-quit, and post-quit changes. A latent variable framework using Mplus 7.4 will allow estimates of treatments on individual growth in mediators (path 'a') to be modeled jointly with effects of growth in likelihood of abstinence (path 'b') using models that limit bias in estimates and provide accurate evaluation of mediation using bias corrected effect estimation and product of coefficients procedures. We will attempt to create a composite that amalgamates all reward processing mediators using principal component analysis (PCA), or if a strong component is not detected, test each raw variable individually. We will model time to lapse first and other smoking outcomes secondarily with and without smoking as a time-vary covariate. Additional multiple mediator models adding all 3 growth pieces simultaneously and including the discriminant constructs (negative affect, urge to smoke to alleviate negative affect) will be test the specificity of effects.

Secondary Aims: Aim 3 will examine medication effects on anhedonia (SHAPS) and related psychopathology (i.e., depressive, social anxiety, ADHD, PTSD symptoms) and body weight and body fat percentage trajectories using individual growth models (intercept and slope) of assessments at visits during treatment. Moderation of the differential effect of treatment (Aim 4) will be assessed with interaction terms of treatment condition and corresponding moderators (SHAPS, depressive, social anxiety, ADHD, PTSD symptoms) in successive models as described above in LGCM.

Supplemental analyses of the biological variable of sex and other characteristics (age, ethnicity/race). Using the strategies above, we will examine if sex, ethnicity/race, and FTND moderate treatment effects on primary and secondary outcomes. We will report sex-stratified analyses and test, amongst women, whether days since menstruation at the onset of treatment and quit day moderates outcome using several classification methods (follicular vs. luteal; early follicular vs. late follicular vs. mid luteal vs. other).

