relapse curves in anhedonic smokers, BUP-450 vs. BUP-300 vs. PLA effects on weight loss and mental health.^{22,97,162} We generated 1,000 multivariate normal random samples of correlated binary outcomes using covariance estimates from prior trial data (range 0.55-0.25)³ and analyzed the datasets using LGCM focusing on the proportion of significant ($p < 0.05$) values for each pair-wise contrast (Aim 1). The percentage of datasets with significant effects for each hypothesis (i.e., $>80\%$ of $ps < .05$) provided a simulation-based estimate of power. Using this technique, we found that enrolling a sample size of 375 (BUP-450: $N < 150$, BUP-300 $N < 150$) conservatively would have power >0.83 to detect main effects when testing our primary hypothesis, allowing for 20% attrition among those enrolled. Parallel simulations were conducted using LGCM to assess power for growth trajectories in continuously scaled mediators assuming an effect of treatment dose response on reward processing ($ds > 0.3$), and reward processing on outcome ($ds > 0.17$) based on the prior literature.^{131,140,201,202} We also found support for power >0.81 with average effects of 0.31 ($sd = 0.11$) with $N = 375$. Additional simulations for secondary mental health and body/weight adiposity outcomes based effects in prior literature ($ds > 0.3$)^{22,97,162} yielded adequate power ($> .80$). Missing individuals will be presumed to have continued smoking. All analyses will use an intent-to-treat approach.

REFERENCES

4. [name] AM, Zvolensky MJ. Anxiety, depression, and cigarette smoking: A transdiagnostic vulnerability framework to understanding emotion-smoking comorbidity. *Psychological bulletin*. 2015;141(1):176.
5. Gorwood P. Neurobiological mechanisms of anhedonia. *Dialogues Clin Neurosci*. 2008;10(3):291-299.

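### The Aim 3 power above .80 in C.8 is reproduced at 375 participants but not at the 300 randomized: weight and body-fat change have about 0.74 at the d = 0.30 floor

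*Combined protocol and SAP*

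**What the plan says.** C.8 gives three power figures. The third covers Aim 3 and opens with "Additional simulations for secondary mental health and body/weight adiposity outcomes based effects in prior literature". It assumes a floor for the effect, "body/weight adiposity outcomes based effects in prior literature ($ds > 0.3", and reports that the simulations "yielded adequate power ($> .80". It gives no N, no SD for scaling d, no visit set and no attrition.

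The neighbouring sentences do give sample sizes. The primary-outcome sentence refers to "enrolling a sample size of 375 (BUP-450: $N < 150$, BUP-300 $N < 150", followed by an allowance of 20% attrition among those enrolled. The mediator sentence, directly before the Aim 3 one, uses N = 375.

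Elsewhere the trial is smaller. The Specific Aims randomize participants to "the standard 300 mg/day dose of bupropion (BUP-300; N=150) or a high 450 mg/day dose (BUP-450; N=150", and C.4 calls 300 randomized smokers the intent-to-treat sample.

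Aim 3(b) concerns "change in body weight and percent body fat composition". C.7 analyses "body weight and body fat percentage trajectories using individual growth models (intercept and slope) of assessments at visits during treatment". C.5 has weight taken at every study visit. The notes to the C.5 schedule mark the adiposity scan only before randomization and at the end-of-treatment visit, whereas C.6 lists adiposity among outcomes assessed at five time points.

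**The concern.** A statement that effects above 0.3 have power above .80 should hold down to 0.3. Whether it does depends on which N was simulated, and the sentence does not say. If it was 375, the printed power belongs to a trial a quarter larger than the one being run (375 / 300 = 1.25).

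The figure matters because A.11 gives the weight and mental-health outcomes a role of their own: if quit rates do not differ, a benefit there would still be presented as a worthwhile result. Readers will therefore rely on the stated chance of detecting such a benefit.

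**Working it through.** **Inputs.** d = 0.30, the floor in C.8. Alpha 0.05, from the Aim 1 simulation ("focusing on the proportion of significant ($p < 0.05$) values for each pair-wise contrast (Aim 1"); two-sided is assumed, because C.8 does not say. Allocation is 1:1 (C.5). N is 375 (C.8) or 300 (Specific Aims, C.4). d is taken in units of the SD of change, which is an assumption.

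**Step 1. Two-arm comparison of change.** With n per arm, power ≈ Φ(d·√(n/2) − 1.960). The exact noncentral-t value is shown beside it.

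| N analysed | n per arm | d·√(n/2) | Normal | Exact t |
|---|---|---|---|---|
| 375 | 187.5 | 2.905 | 0.828 | 0.826 |
| 300 | 150 | 2.598 | 0.738 | 0.736 |
| 240 | 120 | 2.324 | 0.642 | 0.639 |

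C.8's bound is reproduced at 375 and not at 300.

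**Step 2. Where .80 begins.** d = (1.960 + 0.842)·√(2/n). At 150 per arm this is 2.802 × 0.1155 = 0.323. By the exact t, power is 0.796 at d = 0.323, 0.801 at 0.325 and 0.813 at 0.33. At d = 0.30, .80 needs about 176 analysed per arm (exact t 0.801).

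**Step 3. Growth model for weight.** Take eight weighings, at weeks −4, −2, −1, 0, 1, 2, 4 and 8, with time rescaled to run from 0 to 1. The sum of squared deviations of time is then 0.681. Let the slope variance be 1 and the error variance e.

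- Variance of one person's estimated slope: 1 + e/0.681 = 1 + 1.469e.
- Variance of the observed start-to-end change: 1 + 2e.
- Effective d = 0.30·√[(1 + 2e)/(1 + 1.469e)].

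The values of e are assumed, because the plan gives none. Results at 150 per arm (normal approximation):

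| e | Error share of change variance | Complete data | Loss pattern A | Loss pattern B |
|---|---|---|---|---|
| 0.01 | 2% | 0.741 | 0.729 | 0.734 |
| 0.10 | 17% | 0.757 | 0.737 | 0.720 |
| 0.25 | 33% | 0.777 | 0.748 | 0.723 |
| 0.50 | 50% | 0.797 | 0.762 | 0.734 |

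Pattern A borrows the retention that C.4 cites from an earlier 12-month trial: 81.3% complete, 2.3% with baseline only, and the remaining 16.4% assumed lost after week 4. Pattern B assumes that 20% stop after the fifth weighing. Both keep the data collected before dropout, as the maximum-likelihood approach in C.7 does. Eight weighings is a favourable count, since C.5 lets some visits take place by phone.

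**Step 4. Body fat.** With two scans the growth model reduces to the change comparison in Step 1, so power is 0.736 with 300 analysed. A mid-treatment scan would move it towards the weight figures.

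**Step 5. Symptom scales.** If d is on the raw-score SD, the answer depends on the baseline-to-follow-up correlation ρ, which the plan does not give. At 150 per arm with complete data (normal approximation):

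| ρ | Change score, d/√(2(1−ρ)) | Baseline-adjusted, d/√(1−ρ²) |
|---|---|---|
| 0.3 | 0.593 | 0.777 |
| 0.4 | 0.660 | 0.809 |
| 0.5 | 0.738 | 0.851 |
| 0.6 | 0.828 | 0.901 |
| 0.7 | 0.918 | 0.953 |

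The bound may hold or fail.

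**The case against.** The other side has four good arguments.

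- **C.8 gives a floor, not a value.** With complete data, the shortfall at 150 per arm lies between d = 0.30 and about 0.325. This stands and limits the size of the point. It does not remove it, since the sentence claims the bound for every effect above 0.3.
- **The figure is right at C.8's own N.** It is reproduced at 375, so this is less a miscalculation than a consequence of C.8 placing 375 beside arms of 150. That stands. The reader still needs the power of the 300-person trial.
- **The scale and sidedness are unstated.** A one-sided 0.05 test at 150 per arm would give 0.83. With d on the raw-score SD and adjustment for a highly correlated baseline, power would be well above .80 even for weight. The change scale is the natural reading because Aim 3(b) is worded as change, but C.8 does not confirm it.
- **Repeated weights and partial data help.** They do, and Step 3 credits them. Even so, no run in that table reaches .80 at d = 0.30.

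A reader might go further and take 0.64 as the plan's own figure, by removing 20% from 300. The documents do not support that. 375 × 0.80 = 300, so the 20% may already be the step from 375 to 300, and removing it again may count it twice. The 0.64 also counts completers only, whereas C.7 uses all available data. It is a lower bound. Nor does A.11 say that a null secondary result would be read as evidence of no effect; it speaks of an observed benefit.

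**Conclusion.** The point holds in limited form. The Aim 3 power statement is met at 375 but not at the 300 randomized, at its own floor, for change in weight and body fat. Power there is about 0.74 rather than above .80. For weight it runs from 0.74 to just under 0.80 with complete data, and from about 0.72 to 0.76 under the two loss patterns tried. The bound is met from d of about 0.325.

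This rests on a two-sided 0.05 test, on d in units of the SD of change, and, for the growth model, on assumed error variances and dropout times. The simulation behind C.8 cannot be rerun from the text.

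A reader might infer that the power statement is wrong for all Aim 3 outcomes. That does not follow: for the depressive, social anxiety, ADHD, PTSD and anhedonia scales the documents leave the matter open. The point concerns secondary outcomes only and does not bear on the Aim 1 power figure.

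**What to change.** Re-run the Aim 3 simulation at 150 randomized per arm, with the visits at which each outcome will be measured and an explicit rate of loss after randomization. In C.8, then:

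- state the N, the visit set, the attrition, the sidedness of the test and the SD that scales d, with the assumed baseline correlation for the symptom scales;
- say whether the 20% is lost before or after randomization, so that 375 and 300 can be reconciled;
- for weight and body fat, replace the claim of power above .80 with the figure delivered: about 0.74 at d = 0.30 on the change scale before attrition, with a detectable d of about 0.325 at .80 power;
- settle whether body fat is scanned twice or at all the outcome assessments in C.6, because the simulation needs this.

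The cost is one re-run of an existing simulation and a few lines of text. No extra enrolment is needed. The drawback is a slightly less favourable stated power for secondary outcomes.
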